- Arm 3: Azacytidine will be administered subcutaneously (SQ) or intravenously (IV) for 7 days of every cycle with daily schedule of 7 consecutive days (Days 1-7) or for days 5-2-2 which is 5 consecutive weekdays (Days 1-5) with rest on the 2 weekend days (Days 6 and 7) and then dosing the first two weekdays of the next week (Days 8 and 9) of each 28-day cycle as determined by treating physician. Alternative dosing schedules such as 4-2-3 which is 4 consecutive weekdays (Days 1-4) with rest on the 2 weekend days (Days 5 and 6) and then dosing the first three weekdays of the next week (Days 7, 8, and 9) of each 28-day cycle or other schedules allowing the 2 day weekend interruption may be applied as long as we make every attempt to give the 7 days of azacytidine as consecutively as possible. This must be clearly documented in the medical record as determined by treating physician after approval from the PI. Both SQ and IV forms of administration are FDA approved and considered interchangeable. Patients may start receiving 5-azacytidine by one route and changed to the other, and also administration schedules from one schedule and changed to the other at any time as needed based on patient and/or physician preference.

Nivolumab will be administered as an approximately 60 minute IV infusion on Day 8 and Day 22 (+/- 3 days) of each 5-azacytidine cycle for the first 4 cycles or until CR (whichever occurs earlier) followed by a maintenance regimen (one dose of nivolumab on Day 8 of each cycle of 5-azacytdine).

Patients who have evidence of budding relapse or seem to have clinical benefit may continue or revert back to receiving nivolumab on Day 8 and Day 22 (+/-3 days) of each cycle of 5-azacytidine. Patients may receive nivolumab more or less frequently during the maintenance regimen at the discretion of the treating physician only after discussion with the PI.

Nivolumab will be administered every cycle with no interruptions unless there are adverse events as described in Section 5.3.

Venetoclax will be administered orally daily on Days 1-21 of the first cycle; and Days 1-14 for subsequent cycles depending on the dose level being evaluated in the lead in phase (Table 5C).

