- Grade 3 or 4 nausea, vomiting and diarrhea will be considered DLT only if not controlled by optimal therapy.
- Grade 3 biochemical abnormalities (e.g., lipase or bilirubin elevation) will only be considered DLT if accompanied by clinical consequences. Grade 3 or 4 electrolyte abnormalities will only be considered DLT if possibly related to study drug and not corrected by optimal replacement therapy.
- Results in discontinuation of therapy
- Any treatment-related death;

Hematologic DLT is defined as grade ≥ 3 neutropenia and/or thrombocytopenia with a hypocellular bone marrow ($<10\%$ cellularity) lasting for 42 days or more from Cycle 1 Day 1 in the absence of residual leukemia (i.e., with less than 5% blasts or residual leukemia by flow-cytometry or RT-PCR). Anemia will not be considered for the definition of DLT.

-Patients that are removed from study before day 28 for any reason other than toxicity and have not experienced DLT will be replaced. Patients who come off study earlier than 28 days during the DLT evaluation period may continue to receive protocol therapy if they are having clinical benefit, after discussion with the PI. The rationale for continuing therapy must be clearly documented in the patients chart.

-Patients who do not receive venetoclax on day 1 due to logistical and/or financial reasons, the DLT period will be extended to 28 days from the first dose of venetoclax. For evaluation of neutropenia-related DLT, the DLT period will be 42 days from the first dose of venetoclax.

5.2.1.5 Arm 1: We will first treat 6 patients at dose level 0 in the lead-in phase. If DLT occurs in $>/=2/6$ patients, this dose level would exceed the MTD, and 6 patients will be treated at the next lower dose level (i.e. dose level -1). The dose de-escalation (Table 5) will continue in cohorts of 6 until we reach a dose level at which $<2/6$ patients experience a DLT in the first 28 days. The dose level at which 0-1/6 patients experience a DLT in the first 28 days of treatment will be the MTD and will be used to treat an additional patients in the phase II portion of the study. If $>/=2/6$ patients experience DLT at dose level -4, the study will be revised to consider additional lower dose levels (based on potential synergistic toxicity).

If DLT is observed in the first 28 days of treatment in 0 or 1/6 at dose level 0, then dose level 0 will be used for the phase II portion of the study.

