Patients that are removed from study before day 28 for any reason other than toxicity and have not experienced DLT will be replaced.

5.2.1.6 Arm 2: We will first treat 6 patients at dose level 0 in the lead-in phase. If DLT occurs in $>/=2/6$ patients, this dose level would exceed the MTD, and 6 patients will be treated at the next lower dose level (i.e. dose level -1). If DLT occurs in $</=1/6$ patients, this dose level would not exceed the MTD, and 6 patients will be treated at the next higher dose level (i.e. dose level +1). The dose escalation or de-escalation (Table 5b) will continue in cohorts of 6 until we reach a dose level at which $<2/6$ patients experience a DLT in the first 28 days or if $</=1/6$ patients experience a DLT at dose level +1. The highest dose level at which 0-1/6 patients experience a DLT in the first 28 days of treatment will be the MTD and will be used to treat an additional 54 salvage 1 and 2 patients (Arm 2 Salvage Cohort) and 30 frontline AML $>/= 65$ years not candidates for induction therapy (Arm 2 Frontline cohort) in the phase II portion of the study. If $>/=2/6$ patients experience DLT at dose level -2, the study will be revised to consider additional lower dose levels (based on potential synergistic toxicity).

Patients that are removed from study before day 28 for any reason other than toxicity and have not experienced DLT will be replaced.

5.2.1.7 Arm 3: We will first treat 6 patients at dose level 0 in the lead-in phase (part a). If DLT occurs in $>/=2/6$ patients, this dose level would exceed the MTD, and 6 patients will be treated at the next lower dose level (i.e. dose level -1). The dose de-escalation (Table 5C) will continue in cohorts of 6 until we reach a dose level at which $<2/6$ patients experience a DLT in the first 28 days. The dose level at which 0-1/6 patients experience a DLT in the first 28 days of treatment will be the MTD. If $>/=2/6$ patients experience DLT at dose level -3, the study will be revised to consider additional lower dose levels (based on potential synergistic toxicity).

If DLT is observed in the first 28 days of treatment in 0 or 1/6 at dose level 0, then dose level 0 will be the MTD. The RP2D will be selected at the end of the lead-in phase and may be the MTD dose or a dose level lower than the MTD.

Patients that are removed from study before day 28 for any reason other than toxicity and have not experienced DLT will be replaced.

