- During cycle 1, venetoclax will be dose escalated daily to the goal dose of 400mg daily. Patients will receive 100mg on Day 1, 200mg on Day 2 and 400mg on Day 3 and onwards, or adjusted dose if on concomitant azoles (discussed below in section 6.3). Venetoclax dose ramp-up as described in section 6.4.
- If venetoclax is not available at the start of therapy due to different reasons (insurance, financial, transportation, others), azacitidine and nivolumab can start and venetoclax is added when it becomes available.
- If azacitidine cycles are delayed, venetoclax therapy may continue on Days 1-21 of a 4-week cycle after discussion with the PI or Co-PI and documentation in the medical record. If azacitidine cycles are delayed, nivolumab may continue as scheduled (q2 weeks) after discussion with the PI or Co-PI and documentation in the medical record.

5.2.2 One cycle of therapy is defined as 28 days. Patients will receive one cycle of therapy every 28 days (+/- 7 days). The ipilimumab will be given every 6 weeks (+/-3 days).

5.2.2.1 In the expansion (part b) portion of the study (once the MTD/RP2D dose has been defined) cycles may be started early (but not earlier than day 21) for patients with active disease if judged in the best interest of the patient.

Nivolumab and azacytidine

For the lead-in (part a) cohort, DLT defining period is 28 days. As such, cycle 2 should not be started before 28 days for the patients being treated on the lead-in cohort.

5.2.2.2 Subsequent cycles may be delayed for recovery of toxicity or other medical conditions (e.g. infections). Delays in start of subsequent cycles greater than 8 weeks will be acceptable only for patients who are deriving clinical benefit and after discussion with the principal investigator of potential risk/benefit ratio.

5.2.2.3 In instances where one drug has to be discontinued transiently because of safety, the administration of the other drug may continue as scheduled. If the drug that is held can resume at a later time, no doses will be made up and the administration will follow the originally defined schedule calendar according to the drug that was continued.

5.2.2.4 Subsequent courses of 5-azacytidine and nivolumab OR 5-azacytidine with nivolumab and ipilimumab OR 5-azacytidine with nivolumab and venetoclax may be administered regardless of peripheral blood counts during the first 4 cycles and/or in the presence of residual leukemia.

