If prolonged myelosuppression (more than 8 weeks) WITH evidence of a hypocellular marrow (marrow cellularity less than 5% without evidence of leukemia) is observed, 5-azacytidine and nivolumab OR 5-azacytidine with nivolumab and ipilimumab OR 5-azacytidine with nivolumab and venetoclax will be discontinued. Delays in start of subsequent cycles greater than 8 weeks will be acceptable only for patients who are deriving clinical benefit and after discussion with the principal investigator of potential risk/benefit ratio. If the peripheral counts do not recover (ANC <1 x10⁹/L and/or platelets <30 x10⁹/L) but there is evidence of residual leukemia in the bone marrow by morphology or flow-cytometry, subsequent cycles can be administered at the discretion of the treating physician not earlier than 21 days after the prior cycle.

5.2.2.5 For patients who discontinue therapy, the reason for treatment discontinuation will be captured.

5.2.2.6 Patients must receive at least 5 of 7 planned doses of azacitidine, 2 of 2 planned doses of nivolumab and 18 of 21 planned doses of venetoclax during the first 28 days on trial (i.e. during cycle 1) to be considered evaluable

Nivolumab and azacytidine during the DLT phase. Patients who receive less than these doses of each drug during the first 28 days on trial will not be considered evaluable during the DLT phase. However, if such patients develop a toxicity that would normally be considered a DLT this will still be captured as a DLT. Any toxicity that meets the criteria for DLT during the first 28 days of trial in a patient who has received at least one dose of either azacitidine, venetoclax or nivolumab will constitute a DLT. Patients not considered evaluable due to insufficient dosing and who do not develop a toxicity that is considered a DLT will be replaced. These patients may continue therapy on trial after discussion with the PI if they are having clinical benefit and the reasons for continuation and potential benefit/risk profile for the patient must be clearly documented in the medical records. In the expansion phase (part b), DLT will not be monitored. We will perform continuous safety monitoring every 5 patients for “drug-related non-hematological Grade 3/4 AE’s.”

5.2.2.7 Dose modifications other than the ones mentioned above can be considered after discussion with the PI and proper documentation of the rationale.

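### In the Arm 3 lead-in, the 18-of-21 venetoclax minimum in 5.2.2.6 conflicts with the cycle-1 marrow stop and permitted late starts, so some patients treated as directed are replaced

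*Combined protocol and SAP*

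**What the plan says.** Section 5.2.2.6 sets a cycle-1 dose minimum for DLT evaluability: at least 5 of 7 azacitidine doses, and "2 of 2 planned doses of nivolumab and 18 of 21 planned doses of venetoclax during the first 28 days" on trial. Whoever falls short is handled by one sentence: "Patients not considered evaluable due to insufficient dosing and who do not develop a toxicity that is considered a DLT will be replaced". No cause of under-dosing is excepted.

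Four other provisions bear on that minimum.

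- **Marrow-directed stop** (bullets after 5.2.1.7). The cycle-1 marrow is on day 21 +/- 4. Remission or aplasia/hypoplasia stops venetoclax for the rest of the cycle. Without either, venetoclax continues to day 28.
- **Late start** (same bullets). Venetoclax may begin after day 1 for financial or logistical reasons, and this is not a deviation. The text after Table 5C then runs the DLT period for 28 days from the first venetoclax dose, and the neutropenia DLT for 42 days from it.
- **Hematologic DLT** (text after Table 5C). It requires cytopenia with a hypocellular marrow "lasting for 42 days or more from Cycle 1 Day 1 in the absence of residual leukemia".
- **Other replacement rule** (5.2.1.7). "Patients that are removed from study before day 28 for any reason other than toxicity and have not experienced DLT will be replaced".

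The MTD is the level with 0-1 DLTs in six patients (5.2.1.7).

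**The concern.** A dose minimum for evaluability is meant to remove patients whose exposure was too low to test the regimen. Here the protocol itself ends venetoclax early in patients who respond or become aplastic, then treats the resulting shortfall as inadequate dosing. Whether such a patient belongs to the six can therefore depend on response or marrow suppression, which is part of what the lead-in observes. Aplastic patients are also the ones at risk of the hematologic DLT, and that DLT cannot be met before day 42. If they are replaced and a later event is not counted, the lead-in loses the information it most needs on myelosuppression with the triplet.

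The decision is 0-1 versus 2 or more of six, so one patient can change it.

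**Working it through.** **Lead-in size.** Section 11.2 gives 3 levels x 6 patients = 18, which reproduces. The margin in the venetoclax rule is 21 - 18 = 3 doses.

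**Venetoclax doses at a marrow-directed stop.** With start day s and stop day m, doses = m - s if that day's dose is held, and m - s + 1 if it is taken. The minimum is 18.

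| Start | Stop | Doses | Meets 18? |
|---|---|---|---|
| 1 | 17 | 16-17 | no |
| 1 | 18 | 17-18 | only if that day's dose is taken |
| 1 | 19 | 18-19 | yes |
| 3 | 19 | 16-17 | no |
| 5 | 21 | 16-17 | no |
| 8 | 21 | 13-14 | no |

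**Late starts and the 28-day count.** A patient dosed through day 28 without interruption reaches 18 doses only if s is 11 or earlier (28 - 11 + 1 = 18). A start on day 12 gives 17. The DLT period moves with the first venetoclax dose; the dose minimum does not.

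**Same start, different marrow.** Take starts on days 5 to 11 with a day-21 marrow. Without remission or aplasia, dosing to day 28 gives 28 - 5 + 1 = 24 down to 18 doses, and the patient is evaluable. With remission or aplasia, it gives at most 21 - 5 + 1 = 17 down to 11, and the patient is replaced. Only the marrow result differs.

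**DLT capture in a replaced patient.** One sentence of 5.2.2.6 says that a DLT-type toxicity in an under-dosed patient is still captured, with no time limit. The next covers "Any toxicity that meets the criteria for DLT during the first 28 days of trial" in anyone given at least one dose. The hematologic DLT needs 42 days. The first sentence includes it and the second does not mention it.

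**Direction of the effect.** Let d be the DLT rate in all patients, m the share replaced, and h the DLT rate, uncounted, among those replaced. The rate in the counted six is (d - mh)/(1 - m). This exceeds d if h < d and is below d if h > d. Assumed illustration with d = 0.20 and m = 0.10:

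- everyone counted: rate 0.20, P(0-1 of 6) = 0.655
- h = 0: 0.20/0.90 = 0.222, P = 0.601
- h = 0.5: (0.20 - 0.05)/0.90 = 0.167, P = 0.737

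**Toxicity holds below DLT level.** Section 5.3.3 delays nivolumab for most clinically significant drug-related grade 2 or higher non-skin events, so the day-22 dose can be missed. Suppose onset is on day 8 to 22. A 7-day hold misses the day 22 +/- 3 window for onset on days 19-22, or on day 22 only if any dose up to day 28 counts. A 14-day hold misses it for onset on days 12-22, or 15-22.

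Section 2.3 C reports grade 2 immune toxicity in 12% of doublet patients over all cycles, with onset of immune toxicities from 4 days to 3.5 months. If onset is uniform over about 102 days (assumed):

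- 7-day hold: 12% x 1/102 to 12% x 4/102 = 0.1-0.5%
- 14-day hold: 12% x 8/102 to 12% x 11/102 = 0.9-1.3%

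Earlier clustering would raise these.

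With u the share under-dosed for toxicity without a DLT (assumed 2%, 5%, 10%), the DLT rate is d if they are kept as DLT-free, d/(1 - u) if replaced, and d + u if counted as DLTs. P(0-1 of 6) is then:

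| d | Kept | Replaced (as written) | Counted |
|---|---|---|---|
| 0.10 | 0.886 | 0.882, 0.875, 0.863 | 0.844, 0.776, 0.655 |
| 0.25 | 0.534 | 0.522, 0.503, 0.469 | 0.487, 0.420, 0.319 |

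**The case against.** The strongest reply is that the rule is conservative. Replacing DLT-free patients raises the counted DLT fraction, and at a 25% DLT rate it clears a level 1 to 7 points less often than keeping them. That stands. A reader might infer that 5.2.2.6 makes the dose look safer than it is because toxicity holds are discarded. The documents do not support this. The rule looks lenient only against counting holds as DLTs, whereas the protocol sets its non-hematologic DLT threshold mostly at grade 3/4. Counting them would also step down a level with a 10% DLT rate about 4, 10 or 21 points more often than the present rule.

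Holds are probably few as well. Toxicity that leads to discontinuation is already listed as a DLT. Section 5.2.2.3 says of a held drug that "If the drug that is held can resume at a later time, no doses will be made up", but 5.3.3 lets the next nivolumab timepoint move until dosing resumes, which favors the narrower onset windows. Section 2.3 C reports no interruptions among five frontline doublet patients. That is weak evidence, since 0/5 is compatible with a rate up to 1 - 0.05^(1/5) = 45% (one-sided 95%).

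A reader might also infer that 5.2.1.7 and 5.2.2.6 contradict each other. They cover different events, removal from study and under-dosing. They can overlap, and neither is said to govern, but that is a gap in wording only.

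On the marrow stop, the reply is that an on-time starter must have the marrow at the earliest permitted day, and that the 28/42-day wording affects every lead-in patient. Both are true. They limit the size of the problem but do not remove it: late starts are expressly allowed, and the replaced aplastic patient is where the ambiguity matters most.

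Safeguards exist. The RP2D may be set below the MTD, the Medical Monitor sees the cohort summary, all dosed patients enter the safety analysis, and toxicity is monitored every five patients in expansion. None changes the 0-1/6 count, and none requires replaced patients to be listed.

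**Conclusion.** The point holds for the venetoclax minimum. A day-17 stop after a day-1 start leaves 16-17 doses, and a day-5 start with a day-21 stop leaves at most 17. Both patients followed the plan and both are replaced, on the basis of response or marrow suppression. This follows from the text and needs no assumption about rates. How often it occurs is not in the documents. It is narrow for on-time starters (day 17, or day 18 with that day's dose held) and wider for late starters.

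The effect on the MTD decision has no fixed direction. It is stricter if replaced patients have fewer DLTs than the rest, and more lenient if they have more and these go uncounted.

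For toxicity holds the documents support only a limited statement: some such patients are replaced, probably few, and the direction depends on the comparator. They do not show that these holds must count as DLTs. The change is worth making because it is cheap and removes a conflict inside the protocol, not because a large error in the MTD has been shown.

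**What to change.** Amend 5.2.2.6 in three places.

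1. State that a venetoclax stop directed by the cycle-1 marrow neither makes a patient non-evaluable nor is itself a DLT. Apply the minimum only to doses planned from the first venetoclax dose to the directed stop, with at most three missed. Cap the planned number at 21, so that a later stop does not demand more than 18.
2. State that the 42-day hematologic DLT is counted for every dosed lead-in patient, replaced or not, and runs from the first venetoclax dose if the start was late.
3. List every replaced patient, with the reason and the drug held, in the cohort summary before the 0-1/6 decision, so that the Medical Monitor sees any replacement for toxicity.

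Counting sub-DLT toxicity holds as DLTs is optional for the sponsor, given the extra step-downs at acceptable levels.

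The cost is a few sentences, with no added patients at a given level and fewer replacements. There are two side effects to settle. Waiting for day 42 can delay a decision by up to 42 - 28 = 14 days in patients with unresolved aplasia. A very late starter could also be evaluable on few doses: a day-12 start with a day-21 stop has 21 - 12 + 1 = 10 planned. The sponsor may want a floor for such cases.

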11.3 Statistical Design

Part a. Lead-in phase

The MTD is defined as the highest dose level with < 2 out of 6 patients experience a DLT during the first 28 days of treatment. DLT is defined in section 5.2.2. The dosing schema for the combination treatment during the lead in phase is shown in Tables 5 and 5B in section 5.2.1.

Part b. Expansion phase

A. Arm 1 Relapsed/Refractory AML cohort (Aza+Nivo) (N=70: completed accrual and closed to accrual)

Historical data on similar patients show a ORR of 10-15%. The target ORR with the experimental treatment is 30%. This regimen of the combination treatment will be considered worthy of further investigation if it elicits an increase in ORR to 30% with acceptable toxicity. A >30% drug-related grade 3/4 toxicity rate is considered unacceptable. Thus, interim monitoring rules, assuming the prior distributions below, were constructed that meet the following two conditions,

- 1) Stop if $\text{Prob}\{ p(\text{ORR}, E) < p(\text{ORR}, H) + 0.15 \mid \text{data} \} > 0.99$, or
- 2) Stop if $\text{Prob}\{ p(\text{TOX}, E) > 0.30 \mid \text{data} \} > 0.95$,

Where $P(\text{ORR}, E)$ and $P(\text{TOX}, E)$ are the true ORR and toxicity rates for the combination treatment, and $p(\text{ORR}, H)$ is the true ORR rate of the standard treatment. The first rule provides for stopping the study if the data suggest that it is unlikely (i.e., probability < 1%) that ORR rate of the combination treatment is greater than the ORR rate of standard treatment by 15.0%. The second condition will stop the study early if excessive therapy-related grade 3/4 toxicity (>30%) is highly probable (i.e., probability >95.0%) for the combination treatment. Monitoring for toxicity and futility will not begin until 6 patients have been evaluated, and cohort size for future evaluations is 3.

The monitoring rule for the toxicity rate, based on these assumptions and monitoring conditions above is found in Table 9. **For example, accrual will cease if 5 or more patients experience toxicities among the first 6 patients.**

| |
|--|
| Table 9. Stop accrual if the number of drug-related grade 3/4 toxicities is greater than or equal to indicated (i.e., # patients with toxicities) among the number of patients evaluated |
|--|

Nivolumab and azacytidine

| # patients evaluated | 3 | 6 | 9 | 12 | 15 | 18 | 21 |
|----------------------------|-------|-------------------------------------|-------|-------|-------|-------|-------|

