Multi Lean Desktop (version 2.1.0) was used to generate the toxicity and futility stopping boundaries and the OC table (Table 14). In order to utilize the software for the design, a 25% constant rate, and beta(0.5,1.5) priors were assumed for the standard treatment response distribution and experimental treatment response prior distribution, respectively. In addition, a 30% toxicity constant rate and beta (0.6, 1.4) priors were assumed for the standard treatment toxicity constant rate and experimental treatment toxicity prior distribution, respectively.

The probability of stopping the study early if the true ORR of the combination treatment was 30% and the true toxicity rate was 30% was 17.6%. Probabilities of stopping early for high true toxicity rates (i.e., 50%) were 86.5% when the true ORR was 40% and 93.1% when true ORR rate was 25%.

Table 14. Operating characteristics for simultaneous monitoring response and toxicity rates for patients treated with combination treatment

| True Toxicity Rate | True ORR | Prob(stop the trial early) |
|--------------------|-------------|----------------------------|
| 0.10 | 0.25 | 0.5185 |
| | 0.35 | 0.1345 |
| | 0.40 | 0.0558 |
| | 0.45 | 0.0217 |
| | 0.50 | 0.0083 |
| 0.20 | 0.25 | 0.5254 |
| | 0.35 | 0.2975 |
| | 0.40 | 0.0694 |
| | 0.45 | 0.0358 |
| | 0.50 | 0.0226 |
| 0.30 | 0.25 | 0.5797 |
| | 0.35 | 0.2446 |
| | 0.40 | 0.1759 |
| | 0.45 | 0.1461 |
| | 0.50 | 0.1344 |
| 0.40 | 0.25 | 0.7494 |
| | 0.35 | 0.5496 |
| | 0.40 | 0.5087 |
| | 0.45 | 0.4909 |

Table 14. Operating characteristics for simultaneous monitoring response and toxicity rates for patients treated with combination treatment

| True Toxicity Rate | True ORR | Prob(stop the trial early) |
|--------------------|----------|----------------------------|
| 0.50 | 0.50 | 0.4840 |
| | 0.25 | 0.9309 |
| | 0.35 | 0.8759 |
| | 0.40 | 0.8646 |
| | 0.45 | 0.8597 |
| | 0.50 | 0.8578 |

C. Arm 2 First and Second Salvage AML cohort (AZA + Nivo + Ipi)

Historical data on similar patients show an ORR of 12-15%. The target ORR with the experimental treatment is 30%. This regimen of the combination treatment will be considered worthy of further investigation if it elicits an increase in ORR to 30% with acceptable toxicity. A >30% drug-related grade 3/4 toxicity rate is considered unacceptable. Thus, interim monitoring rules, assuming the prior distributions below, were constructed that meet the following two conditions,

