- 5) Stop if $\text{Prob}\{ p(\text{ORR}, E) < p(\text{ORR}, H) + 0.15 \mid \text{data} \} > 0.99$, or
- 6) Stop if $\text{Prob}\{ p(\text{TOX}, E) > 0.30 \mid \text{data} \} > 0.95$,

Where $P(\text{ORR}, E)$ and $P(\text{TOX}, E)$ are the true ORR and toxicity rates for the combination treatment, and $p(\text{ORR}, H)$ is the true ORR rate of the standard treatment. The first rule provides for stopping the study if the data suggest that it is unlikely (i.e., probability $< 1\%$) that ORR rate of the combination treatment is greater than the ORR rate of standard treatment by 15.0%. The second condition will stop the study early if excessive therapy-related grade 3/4 toxicity ($> 30\%$) is highly probable (i.e., probability $> 95.0\%$) for the combination treatment. Monitoring for toxicity and futility will not begin until 6 patients have been evaluated, and cohort size for future evaluations is 6.

The monitoring rule for the toxicity rate, based on these assumptions and monitoring conditions above is found in Table 15. **For example, accrual will cease if 5 or more patients experience toxicities among the first 6 patients.**

Table 15. Stop accrual if the number of drug-related grade 3/4 toxicities is

| # patients | # patients with toxicities |
|------------|-------------------------------------|
| 6 | 5-6 |
| 12 | 7-12 |
| 18 | 9-18 |
| 24 | 12-24 |
| 30 | 14-30 |
| 36 | 16-36 |
| 42 | 18-42 |
| 48 | 20-48 |
| 54 | Always stop with this many patients |

Monitoring the ORR rate, based on the above assumptions and monitoring conditions is found in Table 16. **For example, accrual will cease if no patient experience an overall response within 3 months of initiation of therapy in the first 12 patients treated.**

Table 16. Stop accrual if the number with overall response is less than or

| # patients | # patients with overall response |
|------------|-------------------------------------|
| 6 | Never stop with this many patients |
| 12 | 0 |
| 18 | 0-1 |
| 24 | 0-2 |
| 30 | 0-3 |
| 36 | 0-5 |
| 42 | 0-6 |
| 48 | 0-7 |
| 54 | Always stop with this many patients |

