E. Arm 3 First and Second Salvage AML cohort (AZA + VEN + Nivo) (N=30)

Historical data for salvage patients with azacitidine and venetoclax show an overall response rate (ORR) of 25-50% (DiNardo CD et al, *American journal of hematology* 2018; **93**(3): 401-7; Aldoss I et al, *Haematologica*. 2018 Sep;103(9):e404-e40; Goldberg A et al, *Blood* 2017; **130**(Suppl 1): 1353). It is expected for the current trial that the three-drug combination will improve the ORR by 35% while the toxicity rate is maintained at or below 30%. A sample size of 30 patients ensures that, if the trial is not terminated early, a posterior 90% credible interval for ORR will have width of 0.28 at most, under the assumption of a 60% of ORR rate. The prior probabilities of ORR and toxicity for the experimental regimen are modeled by beta distributions (*Beta* (0.5, 1.5) and *Beta* (0.6, 1.4), respectively). Denoting the historical proportion of overall response rate and toxicity rate by $\{p(\text{ORR},H) = 25\%, p(\text{TOX},H) = 30\%\}$, the following decision criteria will be applied:

- 1) Stop if $\text{Prob}\{p(\text{ORR},H) + \delta_{\text{OR}} > p(\text{ORR},E) \mid \text{data}\} > 0.975$, where $\delta_{\text{OR}} = 0.35$
- 2) Stop if $\text{Prob}\{p(\text{TOX},H) + \delta_{\text{TOX}} < p(\text{TOX},E) \mid \text{data}\} > 0.95$, where $\delta_{\text{TOX}} = 0$

Patients will be monitored in cohorts of 5 according to the following stopping boundaries for overall response and DLT.

| # Patients Evaluated | Stop if this cohort ≤ this # ORR | Stop if ≥ this # toxicities |
|----------------------|-------------------------------------|-------------------------------------|
| 5 | 0-1 | 4-5 |
| 10 | 0-3 | 6-10 |
| 15 | 0-5 | 8-15 |
| 20 | 0-8 | 10-20 |
| 25 | 0-10 | 12-25 |
| 30 | Always stop with this many patients | Always stop with this many patients |

The operating characteristics are summarized in the following table (based on simulations from 10,000 trials).

| True Toxicity Rate | True ORR Rate | PROB(Stop Early) |
|--------------------|---------------|------------------|
| 0.10 | 0.25 | 0.9838 |
| | 0.45 | 0.5615 |
| | 0.60 | 0.1459 |
| | 0.75 | 0.0185 |
| | 0.90 | 0.0011 |
| 0.20 | 0.25 | 0.9840 |
| | 0.45 | 0.5676 |
| | 0.60 | 0.1579 |
| | 0.75 | 0.0322 |
| | 0.90 | 0.0150 |
| 0.30 | 0.25 | 0.9856 |
| | 0.45 | 0.6094 |
| | 0.60 | 0.2393 |
| | 0.75 | 0.1258 |
| | 0.90 | 0.1102 |
| 0.40 | 0.25 | 0.9900 |
| | 0.45 | 0.7297 |
| | 0.60 | 0.4736 |
| | 0.75 | 0.3951 |

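### The Arm 2 expansion toxicity rules count only drug-related grade 3/4 events, so a drug-related death need not count toward stopping; for Arm 3 the counted event is unsettled

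*Combined protocol and SAP*

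**What the plan says.** In the lead-in, the DLT definition in section 5.2.1.4 lists "Any treatment-related death" as a DLT. For the expansion, section 5.2.2.6 states: "In the expansion phase (part b), DLT will not be monitored". It replaces DLT with a check every five patients on each "drug-related non-hematological Grade 3/4 AE".

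Section 11.3 then gives the numerical rules:

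- **A to D (Arms 1 and 2).** Each cohort's text says "A >30% drug-related grade 3/4 toxicity rate is considered unacceptable". Tables 9, 12 and 18 are headed "Stop accrual if the number of drug-related grade 3/4 toxicities is greater than or equal to indicated", and Table 15 opens the same way: "Stop accrual if the number of drug-related grade 3/4 toxicities is". None of them mentions grade 5 or death. Both Arm 1 cohorts (A and B) are marked as closed to accrual.
- **E (Arm 3 salvage).** The cohort is monitored by "stopping boundaries for overall response and DLT".
- **F (Arm 3 frontline).** The boundaries refer to toxicity, with no definition.

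The word non-hematological qualifies the monitored event in 5.2.2.6 but not in 11.3 A to D.

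**The concern.** The protocol grades adverse events by CTCAE version 4.0, and its own background (2.4.2.5) reports a Grade 5 event separately from Grade 3-4 events. Grade 3/4 is therefore not shorthand for grade 3 and above. The plan names treatment-related death where it means to count it, in the lead-in. It then sets that definition aside for the expansion and puts in its place one that does not mention death.

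Applied as worded in Arm 2, a drug-related death with no other qualifying event raises the number evaluated and leaves the toxicity count unchanged, so it moves the cohort away from its limit. In the extreme, six such deaths among the first six patients would score 0 against a limit of 5 (Table 15). At stake is whether the only numerical toxicity rule in the expansion responds to the most serious toxicity. In Arm 3 it is also whether those applying the rule would agree on what to count.

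**Working it through.** **1. Do the printed limits and operating characteristics reproduce?**

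Inputs from 11.3 C: toxicity limit 0.30, prior Beta(0.6, 1.4), posterior cutoff 0.95. With x toxicities in n patients, stop if P(p > 0.30 | Beta(0.6 + x, 1.4 + n − x)) > 0.95.

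- n = 6: x = 4 gives 0.945 and x = 5 gives 0.991, so the limit is 5, as printed.
- n = 48: x = 19 gives 0.913 and x = 20 gives 0.951, so the limit is 20, as printed.
- The other Table 15 limits (7/12, 9/18, 12/24, 14/30, 16/36, 18/42) also reproduce, as do the Arm 3 salvage limits (4/5, 6/10, 8/15, 10/20, 12/25).

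The stop probabilities come from an exact binomial recursion over the looks, with toxicity and response independent:

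- Arm 2 salvage, true ORR 30% and toxicity 30%: toxicity stop 0.1295, futility stop 0.0458. Joint: 1 − (1 − 0.1295)(1 − 0.0458) = 0.1694. Table 17 prints 0.1694.
- Arm 3 salvage, true ORR 60% and toxicity 30%: toxicity stop 0.10979, futility stop 0.14544. Joint: 1 − (1 − 0.10979)(1 − 0.14544) = 0.2393. The plan prints 0.2393.

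The design figures are sound for whatever event is counted. The gap is in the event definition alone.

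**2. What does leaving out deaths do?**

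Let a be the proportion of patients with a drug-related grade 3/4 event and d the further proportion with a drug-related grade 5 event and no other counted event. The counted rate is a as worded and a + d if deaths count. The documents give no value for d, so both a and d are assumptions. As context for a, section 2.3 D reports grade 3/4 immune-mediated toxicity in 6 of 24 evaluable Arm 2 patients (25%). As context for d, section 2.3 C reports one death from immune-mediated toxicity among 51 Arm 1 patients (1/51 = 2.0%), although that event was recorded as grade 4. The 10% value has no source in the documents and serves only as an upper illustration.

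Probability of a toxicity stop from the printed limits, as worded → with deaths counted:

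| a | d | a + d | Arm 2 salvage | Arm 3 (if deaths are excluded) |
|---|---|---|---|---|
| 25% | 2% | 27% | 3.9% → 6.5% | 4.5% → 6.5% |
| 25% | 10% | 35% | 3.9% → 31.6% | 4.5% → 22.4% |
| 30% | 2% | 32% | 12.9% → 19.2% | 11.0% → 14.9% |
| 30% | 10% | 40% | 12.9% → 56.9% | 11.0% → 38.4% |

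For Arm 2 frontline (Table 18) at a = 25%, the change is from 3.6% to 5.6% (d = 2%) or 21.3% (d = 10%). The Arm 3 column applies to both cohorts, whose printed toxicity limits are the same.

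**3. What does Arm 3 count?**

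Section 5.2.2.6 is written around the Arm 3 drugs, and its interval of five patients matches the Arm 3 looks. It says that grade 3/4 events are counted and DLT is not. Section 11.3 E says that DLT is counted, which brings in treatment-related death. Section 11.3 F does not say what is counted. Sections 5.2.2.6 and 11.3 E cannot both hold, so the Arm 3 column above applies only if 5.2.2.6 governs.

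**The case against.** The strongest reply is that few drug-related deaths would escape the count. A patient who dies of a drug effect will often have a grade 3 or 4 event recorded first. The trial's own history fits this: section 2.3 C says one patient died from grade 4 pneumonitis/epiglottitis. The 7 grade 3/4 and 6 grade 2 cases total 13, and the other 12 responded to steroids, so the fatal case lies within the 13 and, being grade 4, within the counted grades. In Arm 2, section 2.3 D attributes no deaths to immune toxicity among 24 evaluable patients. This stands as an argument about size. It does not settle the wording, because whether a death counts then depends on how the event was graded before the patient died.

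Other safeguards exist. Section 9.2 allows termination for the severity of reactions. Section 11.3 requires a safety and efficacy summary for IND Office approval after every five evaluable patients per expansion cohort. Section 10.4 sends all SAEs to the IND Office. A patient who dies before responding would also ordinarily count as a non-responder for futility. These are real, but none sets a numerical toxicity threshold.

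A reader might infer that no expansion rule in any arm can count a death. The documents do not support that: the wording of 11.3 E would count one. A reader might also cite the 5 fatal events among 25 patients in Study M14-387 (section 2.6) as evidence of a high rate. Those are deaths of any cause on a different regimen, and two were disease progression.

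**Conclusion.** The point holds for Arm 2: as worded, the toxicity rules in 11.3 C and D do not count a drug-related grade 5 event unless a grade 3/4 event was also recorded. The closed Arm 1 rules share the wording, but changing them can no longer affect accrual. For Arm 3 the finding is an unresolved conflict over what is counted, not a settled exclusion of deaths.

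The size rests on an assumed rate of otherwise uncounted deaths. At 2% the effect is small, about 2 to 3 percentage points on a 25% grade 3/4 rate. At 10% it is large, but the documents do not support that rate, and the upper figures should not be read as the expected effect. Nor do the documents show that any death on this trial has gone uncounted. Severity: should fix.

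**What to change.** Use one monitored-event definition in 5.2.2.6, in the text of 11.3 C to F and in the headings of Tables 15 and 18: drug-related grade 3 or higher, including drug-related death (grade 3 to 5). In the same amendment, reconcile the DLT wording in 11.3 E with the statement in 5.2.2.6 that DLT is not monitored, define toxicity in 11.3 F, and settle whether the non-hematological restriction, stated only in 5.2.2.6, applies to the rules in 11.3.

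The cost is a wording change. The printed limits and operating characteristics depend on the 30% limit, the prior and the cutoff, so this change needs no recalculation. The downside is that a cohort may stop slightly earlier.
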